14.0 ABBREVIATION LIST	

1.0 OBJECTIVES

Primary:

To assess the response rate within 24 weeks in patients in chronic phase receiving bosutinib with the starting dose of 300 mg per day, with potential escalation to 400mg, 500 mg and 600mg per day.

Response is defined as follows:

- 1. For patients who do not currently have a partial cytogenetic response (PCyR), achievement of major cytogenetic response (MCyR) is considered a response.
- 2. For patients who are currently in PCyR, achievement of complete cytogenetic response (CCyR), CCyR is considered a response.

Secondary:

- Safety of dosing schedule.
- Frequency of treatment interruptions and dose reductions.
- Determine the rate of BCR-ABL/ABL <10% at 3 months and <1% at 6 months, reported
 on the international scale, and the rate of complete cytogenetic response (CCyR) at 6
 months after the start of treatment.
- Determine the cumulative rate of CCyR.
- Determine the rate of major molecular response, MR4, MR4.5 and complete molecular response.
- Determine long-term outcomes, including progression-free survival, event-free survival, and overall survival.
- Investigate the correlation between ABL kinase domain mutations, if present at the time of enrollment, with outcome.

 Determine the rate of development and type of ABL kinase domain mutations during therapy with bosutinib.

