5.0 STUDY ENTRY CRITERIA

5.1 Inclusion criteria:

 Patients with CML in chronic phase who have resistance and/or intolerance to frontline TKI therapy. Resistance is defined as lack (lack defined as response not achieved or lost by the given dates mentioned hereafter) of CHR within 3 months, lack of MCyR within 6 months, and lack of CCyR within 12 months of therapy with frontline TKIs. In addition, loss of MCyR or CCyR at any time during the course of therapy is also considered resistance to therapy. Intolerance is defined as persistent or severe toxicity that is unacceptable to the patient.

- 2. Chronic phase is defined as:
 - a. <15% blasts in peripheral blood and bone marrow;
 - b. <30% blasts plus promyelocytes in peripheral blood and bone marrow;
 - c. <20% basophils in peripheral blood;
 - d. $> or =100 \times 10^9/L \text{ platelets} (> or =100,000/mm3);$
 - e. No evidence of extramedullary disease except hepatosplenomegaly; and
 - f. No prior diagnosis of AP or BP-CML. Patients with clonal evolution but no other criteria for accelerated phase are eligible.
- 3. ECOG performance status of 0, 1, or 2.
- 4. Age 18 years or older.
- 5. Adequate organ function with creatinine less than or equal to 2.0 mg/dl, bilirubin less than or equal to 3.5 mg/dl and ALT less than or equal to 2.5 times institutional upper limit of normal
- 6. Females of childbearing potential must have a negative serum or urine beta human chorionic gonadotrophin (beta-hCG) pregnancy test result within 14 days prior to the first dose of study drugs and must agree to use one of the following effective contraception methods during the study and for 30 days following the last dose of study drug. Effective methods of birth control include: a. birth control pills, shots or implants (placed under the skin by a health care provider) or patches (placed on the skin); b. Intrauterine devices (IUDs); c. condom or occlusive cap (diaphragm or cervical/vault caps) used with spermicide. Females of non-childbearing potential are those who are postmenopausal greater than 1 year or who have had a bilateral tubal ligation or hysterectomy.
- 7. Males who have partners of childbearing potential must agree to use an effective contraceptive method during the study and for 30 days following the last dose of study drug.
- 8. Patients or their legally authorized representative must provide written informed consent.

5.2 Exclusion criteria:

- 1. Women that are pregnant or lactating
- 2. Known to be HIV+

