- 3. Active and uncontrolled disease/infection that in the opinion of the treating physician and principal investigator may affect the ability to participate in the trial or put the patient at unduly high risk
- 4. Unable or unwilling to sign the informed consent document
- 5. Received other investigational therapy within the past 14 days
- 6. Presence of T315I mutation on ABL1 sequencing
- 7. Patient is currently in complete cytogenetic remission (CCyR)

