6.0 TREATMENT PLAN

Bosutinib will be commenced at 300mg/d. Subsequent dose changes may be made in the event of inadequate response or toxicity, according to the dose levels in table 2.

Table 2. Bosutinib dose levels

Dose level	Bosutinib (mg)
+3	600
+2	500
+1	400
Starting dose	300
-1	200
-2	100

6.1 Management of bosutinib dosing.

Patients may have their dose increased by one dose level, at the 1, 3, 6 and 12 month assessments, if they do not achieve or subsequently lose the following therapeutic milestones:

- i) month 1, complete hematologic response;
- ii) month 3, BCR-ABL1 transcripts < or = 10% and/or Ph + metaphases < or = 35%;

- iii) month 6 BCR-ABL1 transcripts < or = 1% and/or Ph + metaphases 0%);
- iv) month 12, BCR-ABL1 transcripts <0.1%. All BCR-ABL targets refer to the international scale.

AND

They do not currently have grade >/= 3 hematologic or grade >/=2 non-hematologic toxicity.

- **6.1.1** Patients who had their dose reduced for any reason may have the dose re-escalated after at least 28 days at the lower dose provided they do not currently have grade >/= 3 hematologic or grade >/=2 non-hematologic toxicity.
- **6.1.2** At least 28 days should have elapsed from a prior dose escalation before a new dose escalation can be implemented, and the patient should not currently have grade >/= 3 hematologic or grade >/=2 non-hematologic toxicity. The highest dose level to be used in this study is 600 mg daily.
- **6.1.3** Dose escalations outside the above timepoints may be initiated by the treating physician if deemed to be in the best interests of the patient, with the approval of the PI.

6.2 Bosutinib dose reductions:

General guidelines include the following:

a) Non-Hematologic Toxicity

- **Grade 2:** Patients with persistent grade 2 toxicity that is unresponsive to appropriate therapy, may have treatment held until the toxicity has resolved to grade < or =1. Bosutinib may then be resumed at the same dose the patient was receiving at the time treatment was interrupted. If the grade 2 toxicity recurs, bosutinib may be held until the toxicity has resolved to grade 1. Treatment may then be resumed with a one dose level reduction.
- Grade 3-4: If a patient experiences Grade 3-4 toxicity that is related to bosutinib,
 therapy must be withheld until the toxicity has resolved to Grade < or = 1. Bosutinib

may then be resumed with a one dose level reduction.

b) Hematologic Toxicity

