The response rate will be estimated along with the 95% credible interval. Data from all subjects who receive any study drug will be included in the safety analyses. The severity of the toxicities will be graded according to the NCI CTCAE v4.0 whenever possible. We will follow standard reporting guidelines for adverse events. Safety data will be summarized by AE category, severity and frequency. The Frequency of treatment interruptions and dose reductions will be summarized. The rates of major molecular response, MR4, MR4.5 and complete molecular response will be estimated along with the exact 95% confidence intervals. Similarly, the rates of BCR-ABL/ABL <10% at 3 months and BCR-ABL/ABL <1% at 6 months since treatment start, on the international scale, will be estimated along with the exact 95% confidence intervals. Kaplan-Meier method will be used to assess the overall survival (OS), failure-free survival (FFS), failure-free survival (FFS) and transformation-free survival (TFS). Cox proportional hazards regression models will be fit to assess the association between patient characteristics including ABL kinase domain mutation status and each survival outcome. In addition, the change of ABL kinase domain mutation status

over time will be summarized and its association with survival outcomes will be analyzed through landmark analyses.

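### The 3-month BCR-ABL <10% rate has no baseline condition, so patients already below 10% at entry count as successes; the same gap at 6 months (<1%) should be small

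*Combined protocol and SAP*

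**What the plan says.** Among the secondary objectives, section 1.0 lists: "Determine the rate of BCR-ABL/ABL <10% at 3 months and <1% at 6 months", on the international scale. The Analysis Plan in section 11.0 repeats this as "the rates of BCR-ABL/ABL <10% at 3 months and BCR-ABL/ABL <1% at 6 months since treatment start", to be estimated with exact 95% confidence intervals. Neither place refers to the BCR-ABL level at entry, and section 11.0 names no denominator for these rates.

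Entry is open to "Patients with CML in chronic phase who have resistance and/or intolerance to frontline TKI therapy" (section 5.1). Intolerance alone is enough. Resistance includes not having reached complete cytogenetic response (CCyR) by 12 months, which a patient in PCyR can satisfy. The only exclusion based on existing cytogenetic or molecular response is in section 5.2: "Patient is currently in complete cytogenetic remission (CCyR". There is no minimum BCR-ABL level.

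For the primary endpoint, section 1.0 does allow for existing response: "For patients who are currently in PCyR, achievement of complete cytogenetic response (CCyR), CCyR is considered a response".

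The dose-escalation milestones in section 6.1 pair the molecular and cytogenetic scales: "month 3, BCR-ABL1 transcripts < or = 10% and/or Ph + metaphases < or = 35" per cent, and "month 6 BCR-ABL1 transcripts < or = 1% and/or Ph + metaphases 0" per cent. Table 4 in section 10.0 makes similar pairings. Table 3 and its footnote 10 require BCR-ABL PCR at screening.

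**The concern.** A rate defined only by an absolute threshold counts two kinds of patient together: those who fall below it on bosutinib, and those who arrive below it on the strength of their previous TKI and stay there. A patient who enters at 6% and is still at 6% at month 3 is a success under the plan as written.

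In a single-arm trial no comparator absorbs this. The 3-month rate then depends partly on how many intolerant or PCyR patients were enrolled. Two cohorts in which bosutinib performs identically could report different rates. The plan saw the same problem for the primary endpoint and solved it by asking PCyR patients for a deeper response, but carried no matching rule to the molecular milestones.

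**Working it through.** **The plan's own figures.** The documents give no expected value for the molecular rates, so there is nothing to reproduce for them. The one design calculation that could be touched is the Simon design for the primary endpoint: 20 patients in stage 1, stop at 4 or fewer responders; 42 in total, success at 12 or more; rates 20% and 35%. Exact binomial calculation gives type I error 0.1009, power 79.75%, early-termination probability 0.630 and expected size 20 + 22 × (1 − 0.630) = 28.1 (28.15 unrounded). The plan states 0.101, 79.8%, 0.63 and 28.2. The design reproduces, and the molecular rates do not enter it.

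**Who can already be below the threshold at entry.**

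| Threshold | Cytogenetic level the protocol sets beside it | Eligible at that level? |
|---|---|---|
| 10% (month 3) | Ph+ at or below 35% (section 6.1, month 3); Ph+ below 35%, labelled major response (Table 4, 6 months) | Yes, if in PCyR (Ph+ 1–35%, section 8.2) |
| 1% (month 6) | Ph+ 0% (section 6.1, month 6; Table 4, 12 months, labelled CCyR) | No: CCyR is excluded |

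Table 4 at 12 months also sets BCR-ABL 1–10% beside Ph+ 1–35%. On the protocol's own pairings, a PCyR patient would tend to enter between 1% and 10%: below the 3-month threshold but not below the 6-month one. The pairings are joined by *and/or* and there is no molecular exclusion, so a few patients could still enter below 1%.

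**Size.** Let n0 of N patients be below the threshold at entry, m the share of those who stay below, and q the rate among the rest.

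All-patient rate = [m × n0 + q × (N − n0)] / N

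The excess over q is (n0/N) × (m − q), which is positive whenever m exceeds q. N = 42 comes from section 4.0. The documents give none of n0, m or q; all three are assumptions. With m = 0.90 and q = 0.40, the excess is 0.5 × n0/42:

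| n0 of 42 | All-patient rate | Rate in those at or above 10% | Difference (points) |
|---|---|---|---|
| 2 | (1.8 + 16.0)/42 = 42.4% | 40% | 2.4 |
| 4 | (3.6 + 15.2)/42 = 44.8% | 40% | 4.8 |
| 8 | (7.2 + 13.6)/42 = 49.5% | 40% | 9.5 |
| 14 | (12.6 + 11.2)/42 = 56.7% | 40% | 16.7 |
| 21 | (18.9 + 8.4)/42 = 65.0% | 40% | 25.0 |

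Other values of m and q move the result. With m = 1 and 20% of patients below at entry, the all-patient rate is 36% when q = 20% (+16 points) and 48% when q = 35% (+13 points).

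For the 6-month rate, suppose 5% enter below 1% (an assumption, chosen small because of the CCyR exclusion). With m = 1, the rate is 24% when q = 20% (+4 points) and 38.2% when q = 35% (+3.2 points).

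**The case against.** Four arguments on the other side have weight.

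*The two milestones are not alike.* A reader might infer that both rates are equally affected. The documents do not support that: the reasoning that puts PCyR patients below 10% also puts them above 1%, and patients in CCyR cannot enter. This stands, and it limits the point mainly to month 3.

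*The plan claims no drug effect.* A reader might infer that carried-over response will be reported as bosutinib effect. Sections 1.0 and 11.0 only say the rates will be determined and estimated. The phrase in section 11.0 about the response rate achieved with bosutinib introduces the primary endpoint. An absolute level at a landmark is also how section 6.1 and Table 4 use these cut-offs, so the all-patient rate is a coherent description. This stands: the fault is that the rate cannot be interpreted alone, not that it is wrong.

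*The pairing is loose.* The scales are joined by *and/or*, and Table 4 at 3 months sets BCR-ABL above 10% beside Ph+ 65–95%. It cannot be said that a PCyR patient is below 10%, only that some may well be. The point needs no more than that.

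*A restricted analysis has its own blind spot.* A reader might conclude that the restricted rate should become the main analysis. That would drop patients who enter below 10% and then rise above it, and so remove failures. This stands, and is why the restricted rate belongs beside the all-patient rate.

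**Conclusion.** The point holds for BCR-ABL <10% at 3 months: eligible patients may already be below the threshold, and nothing in the plan separates them from new responders. For <1% at 6 months the gap exists but should be small.

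The documents do not fix the size. Under 90% retention and 40% conversion it runs from 2.4 points (2 of 42 below at entry) to 25.0 points (21 of 42). A reader might take only the upper part of that range, about 10 to 25 points, as the expected inflation; nothing in the documents rules out the lower part or supports any particular entry count. That these rates apply to all patients is the natural reading, though no denominator is stated.

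The rates are secondary and descriptive, with no null hypothesis and no decision attached. The primary endpoint, the sample size and the go/no-go rule are untouched. The change is worth making because it is cheap and makes the 3-month rate readable in a single-arm trial.

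**What to change.** In the Analysis Plan of section 11.0, keep each all-patient rate with its exact 95% interval, name its denominator, and prespecify beside it:

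- (a) the rate among patients whose screening BCR-ABL on the international scale is at or above the threshold (10% or more for month 3, 1% or more for month 6), with its exact 95% interval;
- (b) the number already below the threshold at entry, and how many of them remain below at the milestone.

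Item (b) keeps in view the patients who lose a level they entered with. Screening results need to be put on the international scale, using the section 8.3 conversion where it applies.

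The cost is a sentence or two of text: screening PCR is already required, so there are no new tests or visits. The restricted rate has a smaller denominator and, at a similar rate, a wider interval. For example, with 8 of 42 below at entry, all staying below, and 12 of the other 34 converting, the all-patient rate is 20/42 = 47.6% (32.0–63.6, width 31.6 points) and the restricted rate is 12/34 = 35.3% (19.7–53.5, width 33.8 points). With 21 below at entry and 7 of the other 21 converting, the widths are 29.9 points (28/42, 50.5–80.4) and 42.4 points (7/21, 14.6–57.0).

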12.0 REPORTING REQUIREMENTS

Reporting Requirements

12.1 Reporting requirements will be as per institutional guidelines.

12.2 Adverse events related to study conditions

The SAE reporting period will begin with the initiation of bosutinib

AEs should be followed to resolution or stabilization, and reported as SAEs if they become serious. This also applies to patients experiencing AEs that cause interruption or discontinuation of investigational product, or those experiencing AEs that are present at the end of their participation in the study. Such patients should receive post-treatment follow-up as appropriate.

12.3 Serious Adverse Event Reporting (SAE)

An adverse event or suspected adverse reaction is considered "serious" if, in the view of either the investigator or the sponsor, it results in any of the following outcomes:

- Death
- A life-threatening adverse drug experience any adverse experience that places
 the patient, in the view of the initial reporter, at immediate risk of death from the
 adverse experience as it occurred. It does not include an adverse experience
 that, had it occurred in a more severe form, might have caused death.
- Inpatient hospitalization or prolongation of existing hospitalization
- A persistent or significant incapacity or substantial disruption of the ability to conduct normal life functions.
- A congenital anomaly/birth defect.

Important medical events that may not result in death, be life-threatening, or require hospitalization may be considered a serious adverse drug experience when, based upon appropriate medical judgment, they may jeopardize the patient or subject and may require medical or surgical intervention to prevent one of the outcomes listed in this definition. Examples of such medical events include allergic bronchospasm requiring intensive treatment in an emergency room or at home, blood dyscrasias or convulsions that do not result in inpatient hospitalization, or the development of drug dependency or drug abuse (21 CFR 312.32).

- Important medical events as defined above, may also be considered serious adverse events. Any important medical event can and should be reported as an SAE if deemed appropriate by the Principal Investigator.
- All events occurring during the conduct of a protocol and meeting the definition of a SAE must be reported to the IRB in accordance with the timeframes and procedures outlined in "The University of Texas M. D. Anderson Cancer Center Institutional Review Board Policy for Investigators on Reporting Unanticipated Adverse Events for Drugs and Devices".
- All SAEs will also be reported in parallel to Pfizer. No individual SAE reports will be sent to Pfizer but SAEs will be reported as a cumulative line listing to BMS approximately every 12 months.
- Serious adverse events will be captured from the time of the first protocol-specific
 intervention, until 30 days after the last dose of drug, unless the participant
 withdraws consent. Serious adverse events must be followed until clinical
 recovery is complete and laboratory tests have returned to baseline, progression
 of the event has stabilized, or there has been acceptable resolution of the event.
- It is the responsibility of the PI and the research team to ensure serious adverse
 events are reported according to the Code of Federal Regulations, Good Clinical
 Practices, the protocol guidelines, the sponsor's guidelines, and Institutional
 Review Board policy.

14.0 ABBREVIATION LIST

ABL – Abelson tyrosine kinase.

AE – adverse event

alloSCT – allogeneic stem cell transplant.

ALT – alanine transaminase.

ANC – absolute neutrophil count

AP – accelerated phase.

AST – aspartate transaminase

ATP – adenosine triphosphate.

BCR – Breakpoint Cluster Region.

BELA – Bosutinib vs Imatinib in Newly Diagnosed Chronic Myeloid Leukemia.

BP - blast phase

BUN – blood urea nitrogen

CBA – chromosome banding analysis

CBC – complete blood count

CCyR – Complete Cytogenetic Response.

CHR – complete hematologic response.

C-KIT – KIT protooncogene

CML - Chronic Myeloid Leukemia.

CP – chronic phase.

CTCAE – Common Terminology Criteria for Adverse Events

DASISION – Dasatinib or Imatinib in Newly Diagnosed Chronic Myeloid Leukemia

EC - ethics committee

ECG - electrocardiogram

ECHO – echocardiogram

ENESTnd – Evaluating Nilotinib Efficacy and Safety in Clinical Trials – newly diagnosed patients

FDA – food and drug administration.

FFS - failure free survival

GI - gastrointestinal

hCG – human chorionic gonadotropin.

HIV - human immunodeficiency virus

INF-a – interferon-alpha.

IRB – institutional review board

IRIS – International Randomized Study of INF-a and STI571

IUD – intrauterine device.

JUN - JUN protocooncogene

LFTs – liver function tests

MCyR – major cytogenetic response

MDASI – M.D. Anderson Symptom Index

MMR – major molecular response

MR4 – Molecular Response with 4 log reduction from baseline BCR-ABL transcript level.

MR4.5 – Molecular Response with 4.5 log reduction from baseline BCR-ABL transcript level.

MUGA - multigated acquisition scan

MYC - MYC protooncogene

NCI – national cancer institute

NK – natural killer.

OS - overall survival.

PCR – Polymerase Chain Reaction

PDGFR – platelet-derived growth factor receptor

Ph - Philadelphia Chromosome

PI – primary investigator

RAF - Rapidly Activated Fibrosarcoma

RAS - Rat Sarcoma

RT-qPCR – real time quantitative polymerase chain reaction

SRC – SRC protooncogene

STAT – Signal Transducer and Activator of Transcription

SUSAR – serious unexpected adverse event

T315I – threonine-315-isoleucine mutation

TEAE – treatment emergent adverse event

TFS – transformation-free survival.

TranscriptionTKIs – tyrosine kinase inhibitors.

ULN – upper limit of normal

WBC - white blood cell
